7.1 Tumor Assessments/Scans

Tumor assessments/imaging studies must be obtained at baseline, at the end of cycle 2 and again after every other cycle (or every 8 weeks, whichever occurs first). After Cycle 6, may be done per institutional standard. The same method of assessment and the same technique should be used to characterize each identified and reported lesion at baseline and during follow-up.

All radiological images must be available for source verification. Images may be submitted for extramural review for final assessment of antitumor activity.

Subjects who come off study should have a final end of study disease-specific assessment done when possible.

7.2 Scan Submission:

All required study scans (CT's, MRI's, MIBG's and PET's) will be de-identified and sent to the NMTRC. All study required de-identified scans will be uploaded to HIPAA compliant database (if available) or sent on disc to:

[name]
NMTRC
Clinical Program Coordinator
[name]
[name]
[contact]
E-Mail: [contact]

7.3 Response Criteria

Overall response rate (ORR) in subjects with radiologically assessable disease will be determined by CT or MRI by cross-sectional imaging, MIBG/PET scans, and/or bone marrow assessment.

Response Assessment: Each subject will be classified according to their “best response” for the purposes of analysis of treatment effect. Best response is determined from the sequence of the objective statuses described below.

Response Criteria for Subjects with Solid Tumors: This study will use the (RECIST) Response Evaluation Criteria in Solid Tumor (version 1.1) from the NCI[44]. Key points are that a maximum of 5 target lesions are identified and that changes in the *largest* diameter (uni-dimensional measurement) of the tumor lesions are used in the RECIST v1.1 criteria.

- **Measurable disease:** The presence of at least one lesion that can be accurately measured in at least one dimension with the longest diameter at least 10 mm (CT scan slice thickness no greater than 5 mm). The investigator will identify up to 5 measurable lesions to be followed for response. Previously irradiated lesions must demonstrate clear evidence of progression to be considered measurable.
- Serial measurements of lesions are to be done with CT or MRI, using the same method of assessment is to be used to characterize each identified and reported lesion at baseline and during follow-up.

- Quantification of Disease Burden The sum of the longest diameter (LD) for all target lesions will be calculated and reported as the disease measurement.
- **Complete Response (CR):** Disappearance of all target and non-target lesions.
- **Very Good Partial Response (VGPR):** Greater than 90% decrease of the disease measurement for CT/MRI lesions, taking as reference the disease measurement done to confirm measurable disease at study entry. Non-target CT/MRI lesions stable to smaller in size.
- **Partial Response (PR):** At least a 30% decrease in the disease measurement, taking as reference the disease measurement done to confirm measurable disease at study enrollment. No new lesions or progression of any non-target measurable lesion.
- **Stable Disease (SD):** Neither sufficient decrease to qualify for PR or sufficient increase to qualify for PD from study entry.
- **Progressive Disease (PD):** At least a 20% increase in the sum of the disease measurements for measurable lesions, taking as reference the smallest disease measurement recorded since the start of treatment (nadir), and minimum 5 mm increase over the nadir or the appearance of one or more new lesions.

Response Criteria for Subjects with Bone Marrow Disease:

- Those subjects with morphologic evidence of disease by routine H and E staining (NSE staining only is not evaluable) will be evaluable to assess bone marrow response.
- **Complete response:** No tumor cells detectable by routine morphology on two consecutive bilateral bone marrow aspirates and biopsies done at least three weeks apart after study entry.
- **Progressive disease:** Tumor seen on morphology on two consecutive bone marrows done at least three weeks apart in subjects who had NO tumor in bone marrow at study entry. (Note: Subject may be declared as progressive disease in bone marrow after only one diagnostic bone marrow at the discretion of the treating physician after discussion with the study chair.)
- **Stable disease:** Persistence of an amount of tumor in the bone marrow by morphology that does not meet criteria for either complete response or progressive disease.

Response Criteria for Subjects with MIBG or PET Positive Lesions

- Subjects who have a positive MIBG or PET scan at the start of therapy will be evaluable for MIBG or PET response. All MIBG's and PET scans will be performed at the research institution and then centrally reviewed.
- **Complete response** = complete resolution of all positive lesions
- **Partial response** = resolution of at least one positive lesion, with persistence of other MIBG positive lesions.
- **Stable disease** = no change in scan in number of positive lesions (includes subjects who have same number of positive lesions but decreased intensity)
- **Progressive disease** = Development of new positive lesions

The intensity of MIBG uptake is not to be considered in the above institutional evaluation.

Duration of response:

Duration of response is defined as the period of time from when measurement criteria are met for complete response (CR) or partial response (PR), whichever is first recorded, until the first date that recurrent or progressive disease (PD) is objectively documented (taking as reference for PD the smallest measurements recorded since the treatment started).

The assessment of response will include the initial measurable targets and will be performed after the second cycle, then after every other cycle (or 8 weeks, whichever occurs first). Serial results of bone marrow aspirates, biopsies and urinary catecholamines will be reviewed for responding subjects to confirm response or lack of progression.

Clinical Response

A subject will be defined as having a clinical response if they have stable disease or better and a decrease in their tumor markers by $\geq 50\%$. Clinical response will also be defined as a subject that has a complete clearing of a previously positive bone marrow while on study.

Progression Free Survival

Time to progression, defined as the period from the first day of administration of study drug until the criteria for progression are met taking as reference the screening measurements, will be assessed.

8 Sample Size Justification

Feasibility

Since this is primarily a feasibility trial, the definition of feasibility for this study will include:

“Enrollment onto study, genomic profile, analysis and report generation completed, tumor board held with treatment decision, treatment review completed, start of treatment, and completion of 1 cycle of therapy.”

Our preliminary results for 5 subjects indicates that we have a sample collection success rate of 5/5 (100%) subjects, a genetic report profile success rate of 5/5 (100%) within the 7-10 day time window as well as a treatment agreement success rate of 5/5 (100%) within the 5 day time window. The average time (+/-SD) for completion of the genetic profile was 6.6 days (+/-1.7 days) with a median of 7 days. The average time (+/-SD) for time to Treatment was 3.2 days (+/-0.8 days) with a median of 3 days. Data preliminary to date for each of these three feasibility markers are very consistent with our anticipated performance standards.

Our initial feasibility trial continues to show that it is feasible and safe to use RNA expression analysis and a DNA mutation panel for tumor boards creating treatment decisions for patients without curative options. This study will ask the feasibility of utilizing DNA exomes and RNA sequencing in a tumor for molecular guided therapy.

Assumptions: The feasibility outcome is a binary measure for each of the three clinical strata with a lower success null value of 50% which would require reconsideration of the full process and an upper success value of 75% for the alternative which would be deemed worthy of further consideration for an efficacy trial at the next phase. A binomial distribution was used for the testing process with a combination of Type I error levels (10%) and Power (75%). The basic design overall is a MiniMax approach which minimizes the overall sample size. **The MiniMax design with an interim look will require an overall sample size of n = 16. Each of the three clinical strata will use a two-stage decision rule.**

The Two-Stage Stopping Rule for each of the three strata is as follows:

Stage 1: Stop and accept the null hypothesis if the observed feasibility rate is less than or equal to 5/9. Otherwise, continue to stage 2.

The probability of stopping for futility is 0.746 when H_0 is true and 0.166 when H_a is true.

Stage 2: Stop and accept the null hypothesis if the observed feasibility rate is less than or equal to 10/16. Otherwise, stop and reject the null hypothesis.

As of Amendment 3.0, 100 subjects have been enrolled and all feasibility measures for all strata have been met. To gain additional feasibility with the new Drug Prediction Report and additional safety and efficacy data, additional subjects will be enrolled to meet a revised goal of 200 total evaluable subjects.

The expanded access for 100 patients will enroll following implementation of Amendment 3.0. Their tumor samples will be analyzed using an updated Drug Prediction Report (Appendix III). Overall Response Rate (ORR) and Progression Free Survival (PFS) for this group will be compared to those of the first 100 patients who received treatment based upon the original Drug Predictiton Report and Pharmacopeia Library.

9 Laboratory Evaluations

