	
targets and will be performed after cycle 2, then after every other cycle.
 
 • A subject will be defined as a responder if CR/PR is observed at any time of the treatment • Clinical response will be seen if stable disease and decrease in tumor markers by $\geq 50\%$ or CR of bone marrow. • Time to progression, defined as the period from the start of the treatment until the criteria for progression are met taking as reference the screening measurements • Comparisons of ORR and PFS for the first and second cohorts of 100 patients (i.e., those who enroll prior to versus after the implementation of Amendment 3.0, respectively) will be performed. 
Safety Measures: Secondary objectives
 
 • Safety analysis will be conducted on all subjects who have received at least one dose of therapy, and will include the frequency of all reported adverse events and laboratory abnormalities as well as frequency of dose interruptions, dose reductions and treatment discontinuation.
STATISTICS/SAMPLE SIZE ESTIMATE	
200 evaluable subjects
 
Patients who enroll following implementation of Amendment 3.0 (second cohort of 100 patients) will have their tumor biopsies analyzed using an updated Drug Prediction Report (Appendix III). Overall Response Rate (ORR) and Progression Free Survival (PFS) for this group will be compared to those of the first 100 patients who received treatment based upon the original Drug Prediciton Report and Pharmacopeia Library.

TABLE OF PROCEDURES AND ASSESSMENTS

Procedure	Screening	Cycle 1 Day 1	Cycle 1 Day 8	Cycle 1 Day 15	Cycle 1 Day 22 (if applicable)	Subsequent Cycles Day 1	Off Therapy/ 30 Day Follow-up
Informed consent	X						
Demographics	X						
Medical history	X	X	X	X	X	X	
Baseline Symptom Form	X	X					
Concurrent meds	X	X				X	X
Physical exam	X	X	X	X	X	X	X
Vital signs	X	X	X	X	X	X	X
Height	X	X				X	
Weight	X	X				X	X
Karnofsky or Lansky play score	X	X		X		X	X
CBC w/diff,	X	X	X	X	X	X	X
Serum chemistry *	X	X		X		X	X
Tumor Markers **	X	X				X	X
Adverse events			X	X	X	X	X
Surgical resection &/or diagnostic biopsy	X						
MRI or CT***	X						
MIBG/PET ***	X						
Bone Marrow (any subject suspected to have BM disease) ^	X						
B-HCG	X						
EKG (as indicated)		X					

* Serum electrolytes, BUN, Creatinine, Bilirubin, ALT, AST

**LDH and/or Specific Tumor Markers for defined disease (if available)

***Type of scan as indicated for disease type

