Following completion of all required screening procedures and certification of all inclusion and exclusion criteria by the Investigator, the coordinator at the NMTRC will be contacted (via e-mail or phone call), at which time the subject will be enrolled in the trial and a unique subject number assigned.

The following screening procedures must be done prior to the first dose of study drug, but are not required to be done before biopsy.

1. MIBG/PET scan (if indicated for tumor type). Other imaging appropriate for tumor type may also be considered.
2. Any subject that is suspected to have possible bone marrow disease: Bone marrow aspirate and biopsy.
3. Completion (by study staff) of pre-study case report forms.
4. Any additional labs or testing required by the tumor board.

For subjects that receive one cycle of treatment while waiting to start tumor board defined treatment (per section 2.11) or if patient did not receive treatment but more than 28 days since last assessment has occurred prior to starting study treatment: The following additional screening procedures must be performed AFTER the last dose of this additional cycle of therapy and PRIOR to the first dose of tumor board defined treatment:

1. Repeat CT or MRI of primary disease sites and any disease sites being followed for study endpoints.
2. CBC with differential- subject must be hematologically recovered to baseline before starting tumor board defined treatment.

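### CT/MRI response is referenced to the enrollment scan even when a later pre-treatment scan is required, and progression has two different references

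*Combined protocol and SAP*

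**What the plan says.** **Response on CT/MRI.** Section 7.3 defines PR as "At least a 30% decrease in the disease measurement, taking as reference the disease measurement done to confirm measurable disease at study enrollment". VGPR is tied to the same confirming measurement, with entry in place of enrollment. SD refers only to study entry. CR requires that every lesion be gone and names no reference measurement. The synopsis (Criteria for Evaluation) adds: "A subject will be defined as a responder if CR/PR is observed at any time of the treatment".

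**Timing of the scans.** Section 4.1, item 4, asks for measurable disease at the time of biopsy. Section 5.2 lists the CT/MRI among procedures due within 21 days before biopsy. Section 2.3 allows the tissue procedure to be a resection, and Section 3.6 allows one cycle of non-study therapy between biopsy and tumor-board treatment. After such a cycle, Sections 3.6 and 5.2 require repeat imaging that includes the sites followed for efficacy. Section 5.2 also requires it, without any interim therapy, if "more than 28 days since last assessment has occurred prior to starting study treatment". It introduces the repeat scan in these words: "The following additional screening procedures must be performed AFTER the last dose of this additional cycle of therapy and PRIOR to the first dose".

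**Progression.** Section 7.3 defines PD on target lesions as a 20% increase, "taking as reference the smallest disease measurement recorded since the start of treatment (nadir), and minimum 5 mm increase over the nadir". Duration of response ends on the same basis, "taking as reference for PD the smallest measurements recorded since the treatment started". Under its Progression Free Survival heading, however, Section 7.3 runs time to progression "until the criteria for progression are met taking as reference the screening measurements". The synopsis agrees with that last wording: "defined as the period from the start of the treatment until the criteria for progression are met taking as reference the screening measurements".

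**Use.** ORR and PFS are secondary objectives (Section 2.2). They are also the two outcomes to be compared between the first and second 100 patients (synopsis; Section 8).

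**The concern.** The protocol collects a scan that separates what happened before the guided regimen from what happened on it, but the response definitions do not use that scan. Resection or an interim cycle can shrink disease after the enrollment scan, and disease can grow while the subject waits. Either change is then scored as if it had occurred on the tumor-board regimen. A subject could be counted as PR with no shrinkage on study, and a real 30% on-study fall could go uncounted.

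The progression wording raises a different problem. Two analysts following different paragraphs of Section 7.3 would date progression differently for the same subject, and PFS would not line up with duration of response. Since ORR and PFS carry the cohort comparison, the reference for each should be settled before that comparison is run.

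**Working it through.** The plan states no figure for this point, so there is none to reproduce. The check applies the plan's own thresholds (PR: 30% decrease; PD: 20% increase and at least 5 mm) to the candidate reference scans.

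**1. PR.** Let s be the share of the enrollment sum of diameters lost before Day 1 (negative s means growth). PR is scored once the current sum reaches 0.70 of the enrollment sum. Measured from Day 1, the on-study change needed is 0.70/(1 - s) - 1.

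| Pre-dose change | Calculation | On-study change needed for PR |
|---|---|---|
| none | 0.70/1.00 - 1 | -30.0% |
| 10% shrinkage | 0.70/0.90 - 1 | -22.2% |
| 20% shrinkage | 0.70/0.80 - 1 | -12.5% |
| 30% shrinkage | 0.70/0.70 - 1 | 0% |
| 20% growth | 0.70/1.20 - 1 | -41.7% |

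For example, 100 mm at enrollment, 80 mm before dosing and 70 mm on study is -30.0% against enrollment (PR) but -12.5% against the pre-treatment scan (SD). In the other direction, 100, 140 and 98 mm is -2.0% against enrollment (not PR) but -30.0% against the pre-treatment scan (PR).

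**2. CR.** With no reference named, lesions resected or cleared before Day 1 and still absent on study can satisfy the definition. This is a second route into ORR that naming a PR reference does not close.

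**3. Progression.** Let n be the on-treatment nadir as a fraction of the screening sum. The PD definition is met at 20% over nadir, subject to the 5 mm minimum. A 20% rise over screening means growth over nadir of 1.20/n - 1: 33.3% at n = 0.9, 71.4% at n = 0.7, and 100% at n = 0.6.

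Take 60 mm at screening, a nadir of 36 mm, then 44 mm, with no new lesion. Against nadir, 44/36 - 1 = +22.2% and +8 mm, which is PD and ends the response. Against screening, 44/60 - 1 = -26.7%, which is not progression; that would need 60 x 1.20 = 72 mm.

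The term for screening measurements is itself open, because Section 5.2 calls the repeat scan a screening procedure. If the older scan is meant, 60 mm there and 72 mm on Day 1 already gives 72/60 - 1 = +20% with no on-study growth. If the repeat scan is meant, it does not.

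**4. Can two scans exist without interim therapy?** Assume the earlier neuroblastoma trial's biopsy-to-treatment time (Section 1.2: 7-20 days, mean 12.4). A scan 21 days before biopsy is then 28 to 41 days old at treatment (mean 33.4). One taken 14 days before biopsy is 21 to 34 days old (mean 26.4). The 28-day rule can therefore apply to unbridged subjects. This shows that it can happen, not how often.

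**5. Scale for ORR, by assumption only.** If a share f of subjects has a repeat scan and a net share q of those changes PR status with the reference, ORR moves by f x q. Assumed f of 10-50% and q of 5-30% give 0.10 x 0.05 = 0.5 points to 0.50 x 0.30 = 15 points. The documents support no value inside that range.

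**The case against.** The strongest reply is that the sponsor probably meant the repeat scan to become the baseline. It must cover the sites followed for efficacy, Section 7.1 speaks of a baseline, and Section 7.3 cites RECIST v1.1. That intent is plausible. But Section 7.1 does not define baseline, the RECIST text is not in the documents, and Section 7.3 writes its own reference for PR and VGPR. What stands is that the text does not show which scan is used in practice.

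On progression, the PFS paragraph speaks of the criteria being met, which can point back to the PD definition. A nadir since the start of treatment also supplies no comparator at the first on-treatment scan, which a screening measurement could provide. This reconciles part of the wording. It does not resolve regrowth after on-treatment shrinkage, where the named references give different answers. Progression by new lesions, marrow or MIBG/PET does not depend on the sum of diameters, so the conflict does not extend to all progression.

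The repeat scan is conditional, so the response problem does not reach every subject by that route. The borrowed timing comes from a gene-chip trial with a 21-day limit on starting treatment, whereas this trial uses exome and RNA sequencing and its feasibility definition has no such limit.

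A reader might infer that ORR is inflated, or that the cohort comparison is biased. The documents support neither. Pre-dose growth lowers ORR just as pre-dose shrinkage raises it, the same definitions apply to both cohorts, and nothing shows that pre-dose change differs between them. Section 12.4 plans exact intervals, Kaplan-Meier plots and exploratory Cox models, which limits the formal weight placed on these outcomes.

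**Conclusion.** The point holds as a defect in the definitions of two secondary endpoints and should be fixed. For CT/MRI disease, PR and VGPR are tied to a scan normally taken at or before biopsy, CR has no reference, and the required repeat scan has no role in scoring response. The on-study change needed for PR ranges from 0% to -41.7% across pre-dose changes from 30% shrinkage to 20% growth. Progression is measured from nadir in one place and from screening in two others, and the results diverge for target-lesion regrowth after shrinkage.

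This rests on reading the definitions literally. The number of subjects with two candidate scans, the size of their pre-dose change, the net direction and any difference between cohorts are not in the documents. The primary feasibility test does not use tumor response and is unaffected; a reader should not extend the point to it.

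**What to change.** In Section 7.3 and the synopsis:

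- Name the last CT/MRI before Cycle 1 Day 1 as the reference for PR, VGPR and SD: the repeat scan where one exists, otherwise the screening scan.
- Count CR only where disease was present at the last pre-treatment assessment.
- Judge ORR evaluability on that pre-treatment assessment by any modality Section 7.3 allows (CT/MRI, MIBG/PET or marrow), so that marrow-only and MIBG/PET-evaluable subjects are not dropped.
- Report ORR under both the enrollment-scan and the pre-treatment reference, in both cohorts, and state before the cohort comparison which is main.
- Flag and count, by cohort, subjects resected or given interim therapy between the enrollment scan and Day 1. Include those resected with no later scan: without interim therapy and treated within 28 days they have no required repeat CT/MRI, so for them the problem remains.
- Reconcile the PD and duration-of-response wording with the time-to-progression wording to one reference, and say which scan the screening measurements are. This review does not choose it, since progression is also a reason for leaving therapy (Section 11.1).

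**Cost.** The change needs a few sentences of text and no new imaging, because Section 7.2 already has study scans sent to the coordinating center. Lesions on repeat scans may have to be measured, as the protocol does not say that they were. ORR may have fewer evaluable subjects. The definition would be clarified after 100 open-label enrollments, which carries its own risk of bias; reporting both versions is the safeguard.

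### Section 7.3 uses non-target lesions to grant or deny response but leaves them out of CT/MRI progression, and does not say whether its bullets or RECIST 1.1 prevail

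*Combined protocol and SAP*

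**What the plan says.** All of the following is in section 7.3 of the combined protocol and SAP.

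- **Targets:** "The investigator will identify up to 5 measurable lesions to be followed for response". All other disease is non-target.
- **Disease measurement:** "The sum of the longest diameter (LD) for all target lesions will be calculated and reported as the disease measurement".
- **PD on CT/MRI:** "At least a 20% increase in the sum of the disease measurements for measurable lesions", measured from the nadir, with a "minimum 5 mm increase over the nadir or the appearance of one or more new lesions".
- **SD:** "Neither sufficient decrease to qualify for PR or sufficient increase to qualify for PD from study entry".
- **CR:** "Disappearance of all target and non-target lesions".
- **VGPR:** "Non-target CT/MRI lesions stable to smaller in size".
- **PR:** "No new lesions or progression of any non-target measurable lesion".

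The same section says that the study uses RECIST version 1.1, picks out some key points of it, and then sets out its own categories. It has no sentence on precedence. Time to progression (given under the PFS label) and duration of response both run until progression is met or documented.

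**The concern.** Three of the five CT/MRI categories look at non-target disease. The progression rule, which stops the PFS and duration-of-response clocks, does not. A child whose target sum is steady while an existing non-target lesion clearly grows is therefore progression-free under the written bullets. If the target markers also fell by half, that child would count towards clinical response, which requires stable disease or better.

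The results at stake are secondary: absolute PFS and duration of response, the comparison with historical PFS in section 12.4, and the comparison with each subject's earlier regimens in section 2.2. Nothing in the documents shows that those comparators were scored under the same progression rule. If they counted non-target growth, the study treatment would look better for that reason alone.

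**Working it through.** **1. Applying the written bullets.** Take a baseline target sum of 100 mm, no new lesion, and clear growth of an existing measurable non-target lesion.

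| Target sum now | Written bullets | If non-target progression counted as PD |
|---|---|---|
| 115 mm (+15%) | SD | PD |
| 100 mm (0%) | SD | PD |
| 80 mm (−20%) | SD | PD |
| 60 mm (−40%) | PR is barred and PD is not met, so no category clearly applies | PD |

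If the growing lesion in the last row is non-measurable, even the PR bar does not operate, because that clause covers only measurable non-target lesions.

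**2. Looking for another route.** Progression on MIBG/PET requires new positive lesions. Marrow progression applies only to subjects with no marrow tumour at entry. Neither reliably catches growth of existing non-target disease. MIBG and PET scans are centrally reviewed, but for radiological images in general section 7.1 makes extramural review only optional.

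**3. Size, first illustration.** The documents do not give the share *f* of first progressions that are non-target only. Assume *f* = 10–30%, exponential PFS, and that this route is never scored, so subjects reach a recorded event only by the two written routes. The hazard becomes (1 − *f*) times the true hazard, and the median is multiplied by 1/(1 − *f*).

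- *f* = 0.10: 1/0.90 = 1.11. A 12-week median reads 13.3 weeks.
- *f* = 0.20: 1/0.80 = 1.25. It reads 15.0 weeks.
- *f* = 0.30: 1/0.70 = 1.43. It reads 17.1 weeks.

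The 12-week median is also an assumption. At 24 weeks (two medians) true PFS is 0.25 and reads 0.25^(1 − *f*) = 0.29, 0.33 and 0.38. These are high-end figures in so far as growing disease soon meets a written route anyway.

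**4. Size, second illustration.** Assume a true median of 16 weeks, scans every 8 weeks (the longest interval in section 7.1 up to cycle 6), and non-target-only progressions recorded one or two scans late. True PFS is 0.707 at 8 weeks and 0.50 at 16 weeks.

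- One scan late: 0.50 + *f*(0.707 − 0.50) = 0.51 at *f* = 5% and 0.56 at 30%.
- Two scans late: 0.50 + *f*(1 − 0.50) = 0.525 at *f* = 5% and 0.65 at 30%.

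For true medians of 8, 16 and 24 weeks and *f* from 5% to 30%, mean PFS restricted to 48 weeks rises by about 0.3 to 4.6 weeks.

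Neither illustration bounds the other. The first model gives 0.50^0.7 = 0.62 at 16 weeks for *f* = 30%, between the one-scan and two-scan results.

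**5. Comparison of the two cohorts.** If *f* is the same in both, each hazard is multiplied by (1 − *f*) under the first model, and the factor cancels from the hazard ratio.

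**The case against.** The strongest reply is that RECIST 1.1 is adopted by name and the bullets can be read as a summary of it. A site might then apply whatever non-target rule the guideline contains, and the numerical effect could be nil. This stands as far as it goes: the documents do not show that sites apply the bullets alone. But they do not say that the guideline overrides the bullets either, and the section adds a category of its own, VGPR. The missing precedence statement is itself a defect, because it allows the same scan to be scored in two ways.

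A second reply is that the PD bullet speaks of measurable lesions, which is looser than target lesions. A measurable sixth lesion, or an irradiated lesion that has clearly progressed, might be thought to be covered. The defined term, disease measurement, points the other way, since it is the target sum.

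A reader might also infer that the comparison of the first and second 100 patients is biased in favour of the treatment. The documents do not support that: both cohorts share the rule, and a contrast between them has no inherently favourable direction. Nor is the main conclusion of the trial in doubt. Feasibility has no progression component, no sample size or error rate depends on PD, and section 12.4 only explores differences from historical PFS.

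**Conclusion.** The inconsistency is real and should be fixed. Read literally, the CT/MRI bullets score clear growth of existing non-target disease as stable, and they leave a target decrease of at least 30% with measurable non-target growth outside both PR and PD. Where they are applied in that way, the direction follows from the definitions: progression is recorded later, and absolute PFS and duration of response are too long. The historical and prior-regimen comparisons may be overstated as well, depending on how their progressions were scored.

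It would go too far to say that reported PFS is overstated throughout the trial, or by any particular amount. How sites resolve the precedence question is unknown, and every size given here rests on an assumed share, median and detection delay.

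**What to change.** For endpoint scoring, in section 7.3:

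1. Add unequivocal progression of existing non-target disease, measurable or not, as a route to CT/MRI PD, beside target-sum growth and new lesions.
2. Align SD with that rule, and remove the restriction to measurable lesions from the non-target clause of PR.
3. State whether the bullets or RECIST 1.1 prevail where they differ.
4. Apply the one rule to both cohorts from the scans already submitted under section 7.2, and report how many PD dates move.

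Progressive disease is also an off-therapy criterion in section 11.1. The sponsor should reconcile that link separately; no rule for stopping treatment is proposed here.

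The cost is a short rewording and a re-check of non-target status on held scans. The re-check is real work, and it may be incomplete after cycle 6, when imaging follows institutional practice. Reported PFS may become shorter. If sites already count non-target progression, few dates will move, and reporting that would settle the question.
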